12.5.4.2 Adverse Events

12.5.4.2.1 All Adverse Events

All AE tables will be presented by product.

A general summary table of AEs will be presented including:

- The number of events and the number and percentage of subjects reporting at least one AE.
- The number of events and the number and percentage of subjects reporting at least one study product –related AE, broken down by product relatedness (related to CHTP / CC) and expectedness.
- The number of events and the number and percentage of subjects reporting at least one AE broken down by severity including each subject only once with his worst severity.
- The number of events and the number and percentage of subjects reporting at least one SAE.
- The number of events and the number and percentage of subjects reporting at least one AE leading to any action taken, broken down by action taken related to the product (product use interrupted, product use reduced, product use withdrawn, none), treatment given (yes, no), study discontinuation, other action taken.

Additional summary tables of AEs will be presented with a breakdown of the number of events, as well as the number and percentage of subjects reporting each AE, categorized by system organ class (SOC) and preferred term (PT) coded according to the Medical Dictionary for Regulatory Activities (MedDRA) dictionary (version 18.0):

- The number of events and the number and percentage of subjects reporting at least one AE.
- The number of events and the number and percentage of subjects with at least one AE related to product exposure and expectedness.
- The number of events and the number and percentage of subjects with at least one AE leading to product discontinuation or reduction.
- The number of events and the number and percentage of subjects with at least one AE leading to study discontinuation.
- The number of events and the number and percentage of subjects with at least one AE related to study procedure.
- The number of events and the number and percentage of subjects with at least one AE by severity (mild, moderate, severe).

If a subject has more than one occurrence of the same AE, the subject will be counted only once within a PT with the worst occurrence based on the presentation (e.g., for presentation by severity = most severe, for presentation by relationship = most related). Missing information on the intensity of AE will be counted as severe.

The data will be presented in the below outputs, the TFL number refers to the TFL number in the accompanying TFL shell document:

TFL number	Title
TABLES	
15.2.6.1	Summary of Adverse Events – Safety Population
15.2.6.2	Summary of Adverse Events by System Organ Class and Preferred Term – Safety Population
15.2.6.3	Summary of Adverse Events by System Organ Class, Preferred Term and Relationship to Study Product Exposure for Investigational Product (CHTP or CC) and Expectedness – Safety Population
15.2.6.4	Summary of Adverse Events Leading to Investigational Product (CHTP or CC) Discontinuation or Reduction by System Organ Class and Preferred Term – Safety Population
15.2.6.5	Summary of Adverse Events Leading to Study Discontinuation by System Organ Class and Preferred Term – Safety Population
15.2.6.6	Summary of Adverse Events Related to Study Procedure by System Organ Class and Preferred Term – Safety Population
15.2.6.7	Summary of Adverse Events by System Organ Class, Preferred Term and Severity – Safety Population
15.2.6.8	Summary of Serious Adverse Events – Safety Population
LISTINGS	

TFL number	Title
15.3.6.1.1	Listing of Adverse Events

Tables 15.2.6.4 - 15.2.6.6 and 15.2.6.8 will only be created if they contain 5 or more events.

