12.5.4 Safety Analysis

In general, all safety data will be listed and tabulated on the safety population by product arm, using the approach described in section [12.1.3](#). Safety variables collected during Exposure Period will also be reported by product exposure.

Adverse event data will serve as the primary assessment of safety. Other safety variables monitored in this study include: respiratory symptoms (cough assessment VAS and Likert scales); vital signs (systolic and diastolic blood pressure, pulse rate, respiratory rate); spirometry; ECG data; clinical chemistry, hematology, concomitant medications, and urine analysis safety panel; physical examination.

The number and percentage of subjects with AEs and SAEs will be tabulated by system organ class and preferred term. Summaries will also be presented for AEs leading to withdrawal, AEs leading to death, AEs by relatedness to product exposure, AEs by severity, and laboratory AEs. Tabulations will be performed for both the number of subjects experiencing an event and the number of events.

The number and percentage of subjects with clinical findings will be tabulated by sequence for laboratory parameters. Shift tables showing change from baseline of clinical findings will be provided for: ECGs, physical examinations, and laboratory parameters (both shifts in normal ranges and toxicity grades). Descriptive statistics will be summarized by visit and change from Baseline for laboratory parameters, ECG, respiratory symptoms, and vital signs.

Confidentiality Statement

Data and information contained in this document are considered to constitute trade secrets and confidential commercial information, and the legal protections provided to such trade secrets and confidential information are hereby claimed under the provisions of applicable law. No part of this document may be publicly disclosed without the written consent of Philip Morris Products S.A.

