12.1.5.1 Insufficient Data for Analysis/Presentation

If there are no values/events at the general value then the break out should not be presented. For example if the number of related AEs is zero then no presentation by severity of related events at the single level will be produced.

Some of the TFLs will not have sufficient numbers of subjects or data for presentation. If this occurs, the blank TFL shell will be presented with a message printed in the center of the table, such as, “No serious adverse events occurred for this study.”

Stratified summaries by sex or daily CC consumption will not be presented if less than 4 subjects are available in one sex or nicotine levels strata.

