12.5.4.2.2 Serious Adverse Events (Including Deaths)

A general summary table of SAEs will be presented using the same approach of AEs (see Section 12.5.4.2 “Adverse Events”), and including the number of events and the number and percentage of subjects reporting at least one SAE broken down by seriousness criteria (fatal, life-threatening, requires hospitalization, results in disability/incapacity, congenital anomaly/birth defect, other medically important event).

SAEs will also be listed in a separate listing by product.

The data will be presented in the below outputs, the TFL number refers to the TFL number in the accompanying TFL shell document:

TFL number	Title
TABLES	
15.2.6.8	Summary of Serious Adverse Events – Safety Population
15.2.6.9	Summary of Serious Adverse Events by System Organ Class and Preferred Term and Severity – Safety Population
LISTINGS	
15.3.6.1.2	Listing of Serious Adverse Events

Tables 15.2.6.8 and 15.2.6.9 will only be created if they contain 5 or more events.

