12.5.4.2.3 Adverse Events Leading to Discontinuation

Summaries will be presented for AEs leading to withdrawal, by product as described in Section 12.5.4.2 “Adverse Events”,

AEs leading to withdrawal will also be listed in a separate listing by product.

The data will be presented in the below outputs, the TFL number refers to the TFL number in the accompanying TFL shell document:

TFL number	Title
TABLES	
15.2.6.5	Summary of Adverse Events Leading to Study Discontinuation by System Organ Class and Preferred Term – Safety Population
LISTINGS	

TFL number	Title
15.3.6.1.3	Listing of Adverse Events Leading to Study Discontinuation

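### A five-event minimum in SAP 12.5.4.2.1 and 12.5.4.2.2 can remove the separate SAE table by SOC/PT and the only specified tabulation of fatal events, which protocol 12.5.4 promises with no minimum

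*SAP*

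**What the plan says.** **Protocol 12.5.4 (Safety Analysis)** sets the commitment. In general, "all safety data will be listed and tabulated on the safety population by product arm". On serious events: "The number and percentage of subjects with AEs and SAEs will be tabulated by system organ class and preferred term". It adds: "Summaries will also be presented for AEs leading to withdrawal, AEs leading to death". None of these carries a minimum count.

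**SAP 12.5.4.2.1 and 12.5.4.2.2** set a condition. The first says "Tables 15.2.6.4 - 15.2.6.6 and 15.2.6.8 will only be created if they contain 5 or more events"; the second says "Tables 15.2.6.8 and 15.2.6.9 will only be created if they contain 5 or more events". The tables concerned are:

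- 15.2.6.4: AEs leading to product discontinuation or reduction
- 15.2.6.5: AEs leading to study discontinuation
- 15.2.6.6: procedure-related AEs
- 15.2.6.8: the general SAE summary, with the breakdown by seriousness criterion
- 15.2.6.9: SAEs by SOC, PT and severity

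**Other SAP sections** assume the outputs exist. For AEs leading to discontinuation, 12.5.4.2.3 says "Summaries will be presented for AEs leading to withdrawal, by product". For outputs with too little data, 12.1.5.1 says "the blank TFL shell will be presented with a message printed in the center of the table", and its example message is for a study without SAEs. Sections 13.2 (safety reporting) and 13.3 (topline results) list 15.2.6.4 to 15.2.6.6 and 15.2.6.8 unconditionally.

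**The concern.** Safety monitoring is a stated secondary objective (protocol 3.2), and protocol 2.1.2 says that CHTP 1.0 itself has not been studied clinically. The protocol undertakes to show serious events by term and to summarise deaths, however few there are. Under the SAP, whether those displays exist depends on the observed number of events, and they fall away at the low counts where each event is worth showing clearly.

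The change is also undeclared. SAP Section 9 gives reasons for dropping the safety shift tables and even for a change of preposition in the creatinine endpoints, but does not mention this rule. A programmer cannot satisfy the condition, the sections that promise the summaries, and the unconditional lists in 13.2 and 13.3 all at once.

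**Working it through.** **Step 1. What remains and what is lost with 1 to 4 events.**

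| Content | Protocol 12.5.4 | SAP output | With 1 to 4 events |
|---|---|---|---|
| SAE events, n and % of subjects, by product | yes | 15.2.6.1 | remains |
| SAEs by SOC/PT, shown separately | yes | 15.2.6.9 | lost |
| SAEs within all AEs by SOC/PT and by severity | yes, as AEs | 15.2.6.2, 15.2.6.7 | remains, not separated |
| SAEs by seriousness, including fatal | deaths promised | 15.2.6.8 | lost |
| Overall count of AEs leading to study discontinuation | yes | 15.2.6.1 | remains |
| The same by SOC/PT | format not specified | 15.2.6.5 | lost |
| Product discontinuation or reduction by SOC/PT | reduction not promised | 15.2.6.4 | lost |
| Procedure-related AEs | not promised | 15.2.6.6 | lost |
| Individual events | yes | Listings 15.3.6.1.1 to 15.3.6.1.3 | remain |

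The row in 15.2.6.1 is specified as "The number of events and the number and percentage of subjects reporting at least one SAE". The contents described for that table include no count of deaths. SAP Table 10 defines a fatal category, but among the AE tables described only 15.2.6.8 is said to use it.

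**Step 2. How often the SAE tables would be absent.** The plan states no figure to reproduce.

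Inputs:
- n = 80 randomised (protocol synopsis and 12.2).
- Threshold of 5 (SAP 12.5.4.2.1 and 12.5.4.2.2).
- SAE rate p per subject: not in the documents. Assumed range 0.5% to 10%, one SAE per affected subject, subjects independent.

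Formula: P(X ≥ 5) = 1 − Σ(k = 0 to 4) C(80, k) p^k (1 − p)^(80−k).

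At p = 2%, the terms for k = 0 to 4 are 0.1986, 0.3243, 0.2614, 0.1387 and 0.0545. Before rounding they sum to 0.9776, so P(X ≥ 5) = 0.0224. P(X ≥ 1) = 1 − 0.1986 = 0.8014. P(1 to 4) = 0.8014 − 0.0224 = 0.7790. Given at least one SAE, the tables are absent with probability 0.7790 / 0.8014 = 97.2%.

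| Assumed rate | Expected SAEs | P(5 or more) | P(1 to 4) | Tables absent, given at least 1 SAE |
|---|---|---|---|---|
| 0.5% | 0.4 | 0.006% | 33.0% | 99.98% |
| 1% | 0.8 | 0.13% | 55.1% | 99.8% |
| 2% | 1.6 | 2.2% | 77.9% | 97.2% |
| 3% | 2.4 | 9.3% | 82.0% | 89.8% |
| 4% | 3.2 | 21.6% | 74.5% | 77.5% |
| 5% | 4.0 | 37.1% | 61.2% | 62.3% |
| 6% | 4.8 | 52.8% | 46.5% | 46.8% |
| 10% | 8.0 | 91.2% | 8.8% | 8.8% |

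P(X ≥ 5) reaches 50% at p = 5.8%, or 80 × 0.058 ≈ 4.7 expected events. The safety population includes everyone who took the product test at Admission, so it can exceed 80. With 100 or 120 subjects (assumed) the break-even rate is 4.7% or 3.9%.

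**Step 3. An example.** Four SAEs on CHTP and none on CC is 4/40 = 10% against 0/40. Four is below five, so 15.2.6.8 and 15.2.6.9 are not created. Table 15.2.6.1 would still show 10% against 0%. The terms would be separated from other AEs, and a death identified as such, only in the listings.

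**The case against.** The strongest reply is that little information is lost. Table 15.2.6.1 has no minimum and is presented by product, the listings are complete, and with one to four events a listing is easy to read. No estimate is biased. This stands, and it rules out a reading a reader might be tempted to make: that serious events would go untabulated by arm.

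Other inferences also go further than the documents allow:

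- **Zero SAEs gives a table page and one to four give none.** This is one reading of 12.1.5.1 beside the minimum. The specific rule may override the general one, or the minimum may define what counts as insufficient data, in which case a shell with a message would appear. The sections need reconciling, but the paradox is not established.
- **The count is pooled over arms.** The SAP does not say. The calculation above counts events across the whole table; a per-arm count would be harder to reach.
- **One to four SAEs is the most likely result.** At 0.5% there is a 67% chance of none (1 − 0.3304).
- **All the conditional tables would usually be missing.** The calculation covers SAEs only. Procedure-related AEs could well reach five, and the protocol does not promise that table.

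For withdrawals, the protocol fixes no format, so the discontinuation row of 15.2.6.1 may fairly be called the promised summary. For separate SAEs by SOC/PT and for deaths, the SAP specifies no such unconditional substitute.

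**Conclusion.** The point holds as a reporting defect. Followed as written, the SAP makes a protocol-promised table (SAEs by SOC/PT) and the only specified tabulation of fatal events depend on the observed count, without declaring it and against other parts of the SAP. The SOC/PT breakdown of AEs leading to discontinuation is lost as well.

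The size depends on an SAE rate the documents do not give. With 80 subjects and one SAE per affected subject, the dedicated SAE tables are more likely than not to be absent below about 5.8% of subjects, and below a lower rate if the safety population is larger. Given at least one SAE, the chance that they are absent is 99.8% at an assumed 1% and 62.3% at 5%. SAE and discontinuation totals by product and all individual events are unaffected. The change is worth making because it costs so little.

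**What to change.** Remove the minimum at least for Tables 15.2.6.5, 15.2.6.8 and 15.2.6.9. The simplest way is to delete the sentence in SAP 12.5.4.2.2 and the matching one in 12.5.4.2.1. Produce these tables by product at any non-zero count, with number of events and n (%) of subjects, and use the 12.1.5.1 message when there are none.

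If a minimum is kept for 15.2.6.4 and 15.2.6.6, declare it in Section 9 with a reason, state whether events are counted over both arms or per arm, and mark those tables as conditional in 13.2 and 13.3.

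The cost is a few lines of SAP text and three short tables, or five if the rule is removed altogether. All are already named in the SAP, and no data collection changes.

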12.5.4.2.2 Serious Adverse Events (Including Deaths)

A general summary table of SAEs will be presented using the same approach of AEs (see Section 12.5.4.2 “Adverse Events”), and including the number of events and the number and percentage of subjects reporting at least one SAE broken down by seriousness criteria (fatal, life-threatening, requires hospitalization, results in disability/incapacity, congenital anomaly/birth defect, other medically important event).

SAEs will also be listed in a separate listing by product.

The data will be presented in the below outputs, the TFL number refers to the TFL number in the accompanying TFL shell document:

TFL number	Title
TABLES	
15.2.6.8	Summary of Serious Adverse Events – Safety Population
15.2.6.9	Summary of Serious Adverse Events by System Organ Class and Preferred Term and Severity – Safety Population
LISTINGS	
15.3.6.1.2	Listing of Serious Adverse Events

Tables 15.2.6.8 and 15.2.6.9 will only be created if they contain 5 or more events.

12.5.4.2.3 Adverse Events Leading to Discontinuation

Summaries will be presented for AEs leading to withdrawal, by product as described in Section 12.5.4.2 “Adverse Events”,

AEs leading to withdrawal will also be listed in a separate listing by product.

The data will be presented in the below outputs, the TFL number refers to the TFL number in the accompanying TFL shell document:

TFL number	Title
TABLES	
15.2.6.5	Summary of Adverse Events Leading to Study Discontinuation by System Organ Class and Preferred Term – Safety Population
LISTINGS	

TFL number	Title
15.3.6.1.3	Listing of Adverse Events Leading to Study Discontinuation

12.5.4.2.4 Laboratory Abnormalities

Laboratory abnormality data will be listed ordered by product, subject, parameter and time point. Details related to the toxicity grading of laboratory abnormalities are available in Section 12.5.4.4.

The data will be presented in the below outputs, the TFL number refers to the TFL number in the accompanying TFL shell document:

TFL number	Title
LISTINGS	
15.3.6.4	Listing of Clinical Chemistry Data, Shift, Changes from Baseline and CTCAE grades
15.3.6.5	Listing of Hematology Data Shift, Changes from Baseline and CTCAE grades
15.3.6.6	Listing of Urinalysis Data Shift, Changes from Baseline and CTCAE grades

12.5.4.3 CHTP Product Quality Complaints

All events relating to the device type will be listed for each subject.

A summary table of product quality complaints will be presented by product, including:

- Number of product quality complaints and the number and percentage of subjects reporting at least one product quality complaint.
- Number of product quality complaints and the number and percentage of subjects categorized by product quality complaint (Defect CHTP 1.0 before use: [REDACTED])

[REDACTED]

Product quality complaints will be listed by product. Data collected during Screening will be listed but not summarized.

The data will be presented in the below outputs, the TFL number refers to the TFL number in the accompanying TFL shell document:

TFL number	Title
TABLES	
15.2.6.10	Summary of CHTP Product Quality Complaints – Safety Population
LISTINGS	
15.3.6.2	Listing of CHTP Product Quality Complaints

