6.6 Investigational Product Accountability and Compliance

6.6.1 Dispensing Investigational Product

From Day -3 onwards to Day 5, the Investigational Product (IP) CC, and from Day 1 onwards to Day 5, the IP CHTP, will be dispensed to the subjects stick by stick. One will be allowed at a time and documented in an appropriate log.

On each day of the confinement period, the time of dispense and return for each product (CC/CHTP 1.0) use has to be documented from Day -3 for CC and from Day 1 for CHTP 1.0 onwards.

CHTP 1.0 will not be promoted for commercial distribution or test market.

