4. To describe the changes in CYP1A2 enzymatic activity in smokers switching from CC to CHTP 1.0, and in smokers continuing to use CC.

Related Endpoint (Day 5):

Molar metabolic ratio of paraxanthine/caffeine (CAF) in plasma.

5. To describe the daily CHTP 1.0/CC consumption over the Exposure Period in smokers switching from CC to CHTP 1.0 as compared to smokers continuing to use CC.

Related Endpoint (Day 1 to Day 5):

Number of CHTP 1.0 and CC used each day for each subject.

6. To monitor the safety profile during the study:

Related Endpoints:

Incidence of adverse events (AEs)/ serious adverse events (SAEs).

Incidence of CHTP 1.0 malfunctions and misuse, including the incidence of heat source drop off.

Respiratory symptoms: cough assessment by visual analogue scale (VAS). Likert scales, and one open question.

Vital signs.

Spirometry.

Electrocardiogram (ECG).

Clinical chemistry, hematology, and urine analysis safety panel.

Physical examination.

Concomitant medications.

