10.5 Safety Population

The Safety Population consists of all the subjects who had at least one exposure to CHTP1.0 (product test at Admission Day). Subjects in the Safety Population will be analyzed according to actual exposure.

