12.1.3 Descriptive Statistics

For continuous data, summary statistics will include the number of subjects (n), the number and percent of subjects with missing data, the arithmetic mean, arithmetic SD, median, first and third quartiles, minimum, maximum, and number; for log-normal data the geometric mean and geometric CV will also be presented. For categorical data, frequency counts and percentages will be presented. Data listings will include all subject level data collected unless otherwise specified. Summary statistics and statistical analyses will generally only be performed for subjects included in the relevant analysis population. For the calculation of summary statistics and statistical analysis, unrounded data will be used.

Summaries on the Safety Population will be produced by actual exposure. Subjects who tested the product but were discontinued before randomization will be shown in a separate column /table.

The following product labels will be used throughout the TFLs (**Table 17**):

Table 17: Product Labels		
Product	Format used in TFLs	Order in TFLs
Carbon Heated Tobacco Product	CHTP	1
Conventional cigarettes	CC	2

The following stratification labels (**Table 18**) for the TFLs will be used:

Table 18: Stratification Labels	
Stratification Factor	Definition
Sex	male
	female
Daily CC consumption (per day)	<10 ¹
	10-19
	>19

¹ Note that due to inclusion criteria for the study there should not be any subjects with daily CC consumption < 10, therefore this category will not be presented unless there is sufficient data for analysis/presentation (see Section 12.1.5.1 "Insufficient Data for Analysis/Presentation").

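### CHTP product complaints are summarised per subject with no rate per stick, and the Day -3 product test is not separated from the Exposure Period

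*SAP*

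**What the plan says.** SAP 5.2 lists as a secondary safety endpoint the "Incidence of CHTP 1.0 malfunctions and misuse, including the incidence of heat source drop off". It gives no unit for incidence.

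SAP 12.5.4.3 gives the summary. "A summary table of product quality complaints will be presented by product, including" two items. The first is the "Number of product quality complaints and the number and percentage of subjects reporting at least one product quality complaint"; the second gives the same quantities by complaint category. The only table is 15.2.6.10, "Summary of CHTP Product Quality Complaints – Safety Population".

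SAP 10.5 defines the population: "The Safety Population consists of all the subjects who had at least one exposure to CHTP1.0 (product test at Admission Day"). It adds: "Subjects in the Safety Population will be analyzed according to actual exposure". SAP 12.1.3 uses two product labels, CHTP and CC, and adds one rule: "Subjects who tested the product but were discontinued before randomization will be shown in a separate column /table".

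On exposure, Protocol 7.3.4 allows up to 5 CHTP sticks in the Day -3 test and sets no minimum. SAP 6.1 then gives 5 days of ad libitum use of the assigned product. Under Protocol 6.6.1, CHTP from Day 1 to Day 5 "will be dispensed to the subjects stick by stick" and is logged. SAP 12.4 summarises product-test use and daily use separately, in Table 15.2.2.1 for the Safety Population.

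**The concern.** A complaint about CHTP needs a CHTP stick in hand, so the number of chances for a complaint is the number of sticks handled. The planned percentage has subjects in its denominator, and those subjects differ greatly in sticks handled: between arms by design, and within the CHTP arm because use is ad libitum. The same product quality can therefore give very different percentages, and a percentage from this study cannot be carried over to a setting with different consumption.

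The endpoint is a named one. Protocol 2.3.4 says that an unexpected malfunction may carry unforeseeable risk, and Protocol 2.1.2 says that CHTP 1.0 has not been studied clinically before. SAP 13.2 sends Table 15.2.6.10 to the sponsor's medical safety officer after database lock. A reader of that table will want to know how often the product fails, and the planned percentage does not answer that.

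**Working it through.** The documents give no malfunction rate or expected complaint count, so there is no stated figure to reproduce. The check has two parts.

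**1. Which complaints and subjects enter the table**

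- Every randomised subject who took the Day -3 test is in the Safety Population, including those later in the CC arm (SAP 10.5).
- SAP 12.5.4.3 leaves Screening data out of the summary. Under SAP 6.1, Screening ends at Admission on Day -3 and the test follows enrolment that day. The exclusion therefore does not clearly remove test complaints.
- For a Day -3 complaint from a subject later in the CC arm, two readings are open. If columns follow the product used after randomisation, the complaint sits under CC. If actual exposure is judged at the time of the event, it sits under CHTP. The SAP does not choose.
- Subjects who tested the product but left before randomisation are dealt with: they have their own column or table.

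**2. Size of the effect of stick numbers (illustration)**

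From the documents: at most 5 test sticks, 5 exposure days, and about 40 subjects per arm.

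Assumed, not in the documents: 10 to 20 CHTP sticks per day; all 5 test sticks used; a complaint probability *p* per stick that is the same for all sticks and subjects and independent between sticks.

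Sticks per subject:
- CC arm: 5.
- CHTP arm: 5 + 5 × 10 = 55, to 5 + 5 × 20 = 105.

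Probability that a subject has at least one complaint in *m* sticks: 1 − (1 − *p*)^*m*.

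At *p* = 0.5%:
- CC arm: 1 − 0.995^5 = 2.5%.
- CHTP arm, 55 sticks: 1 − 0.995^55 = 24.1%.
- CHTP arm, 105 sticks: 1 − 0.995^105 = 40.9%.

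| *p* per stick | CC arm, 5 sticks | CHTP arm, 55 sticks | CHTP arm, 105 sticks |
|---|---|---|---|
| 0.1% | 0.5% | 5.4% | 10.0% |
| 0.5% | 2.5% | 24.1% | 40.9% |
| 1% | 4.9% | 42.5% | 65.2% |
| 5% | 22.6% | 94.0% | 99.5% |

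If a CC-arm subject tried only one stick, the CC figure at *p* = 0.5% would be 0.5%.

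Expected complaints per stick at *p* = 0.5%, with 40 subjects per arm:
- CC arm: 40 × 5 × 0.005 = 1.0 complaint in 200 sticks, or 5 per 1,000.
- CHTP arm, 55 sticks each: 40 × 55 × 0.005 = 11.0 in 2,200 sticks, or 5 per 1,000.
- CHTP arm, 105 sticks each: 40 × 105 × 0.005 = 21.0 in 4,200 sticks, or 5 per 1,000.

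The per-stick rate recovers the common quality level. The percentage of subjects differs about 10- to 16-fold between arms (24.1/2.48 to 40.9/2.48), and it moves from 24% to 41% within the CHTP arm on consumption alone.

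**The case against.** The case for leaving the table alone has weight. The SAP tabulates the number of complaints as well as the percentage of subjects. Table 15.2.2.1 gives stick use on the same population, and SAP 13.2 sends both tables in one package, so a crude rate could be derived. With no unit stated for incidence, number and percentage of subjects is a legitimate descriptive choice, and it matches the adverse event tables. No test uses this table, nobody would take CC as a comparator for CHTP malfunction, and Protocol 8.7 routes any malfunction that leads to an adverse event through the normal reporting process. All of this stands, and it limits the importance of the point. What does not follow is that the rate is already available: deriving it needs matching columns and periods in the two tables, and the SAP does not guarantee that.

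A reader might also infer more than the documents support:

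- **That CC-arm subjects' test complaints will be reported under CC.** This is one plausible reading of a by-product layout, but the text equally allows CHTP. The layout is in a separate shell document that is not available here. The defect is the missing rule.
- **That CC-arm subjects dilute the CHTP percentage.** If columns follow arm, they enter only the CC denominator. A combined figure would be diluted, but SAP 12.5.4.3 does not mention one.
- **That complaints can arise only from sticks used.** SAP 12.5.4.3 has a category for a defect found before use, so sticks dispensed or handled is the better unit.

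The complaint categories are partly redacted, so whether heat source drop-off has its own row cannot be judged.

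**Conclusion.** The point holds as a cheap improvement to a descriptive safety table. The documents establish three things: the planned percentage is per Safety Population subject, exposure to CHTP sticks differs by design between those subjects, and neither a per-stick rate nor a split by period is planned. They also leave open where a Day -3 complaint from a later CC-arm subject is counted.

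The size (24-41% against 2.5% at the same per-stick rate) rests wholly on assumed consumption and an assumed, constant, independent complaint rate. It shows the direction and scale of the problem and does not predict this study's results. The direction needs only that CHTP-arm subjects handle more sticks. The primary endpoints and the study's hypothesis tests are unaffected.

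**What to change.** In SAP 12.5.4.3 and Table 15.2.6.10:

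- Add complaints, in total and by category, per 1,000 CHTP sticks dispensed or handled, and print the number of sticks as the denominator.
- Show the Day -3 product test separately, with all testers in one column. This settles where a test complaint from a later CC-arm subject belongs.
- Show the Exposure Period for CHTP users only, with no CC column.
- Keep the number and percentage of subjects as a second line.

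The cost is a few lines of SAP text and one changed table shell. No new data should be needed. Exposure Period sticks are logged one by one (Protocol 6.6.1). Sticks used in the Day -3 test are collected for accountability (Protocol Table 7), and product-test details are listed and summarised under SAP 12.4. Splitting by period assumes that the product issue log in Protocol 8.7 dates each complaint, which should be confirmed.
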